	Independent Safety Evaluation: Independent safety evaluation will be conducted by a licensed physician who is not involved in the VentaProst COVID-19 clinical study or the sponsoring organization.
Statistical Methods	All patients who are enrolled in the study and who receive at least one dose of study drug will be included in the intent-to-treat (ITT) analyses of pharmacodynamic and safety data. All available data will be used and missing data will not be estimated or carried forward in any statistical summary or analyses.
	Descriptive summary statistics include the number of patients, mean, median, percent coefficient of variation (% CV) (if required), standard deviation, and minimum and maximum values (quantitative variables) or the number of patients and percentages by category (qualitative variables). Changes will be assessed as the difference between baseline measurements and the appropriate post-dose measurements unless otherwise specified. Mean differences between active and historical control groups will be assessed and significance will be determined on the basis of a 95% CI.
	No formal estimate of the sample size has been made. This is an exploratory study and the number of patients was selected to enable an adequate clinical assessment of pharmacodynamic, safety, and tolerability parameters without presenting undue risk to a large number of patients.
Efficacy Analysis	Efficacy will be secondarily determined by summarizing success or failure to meet any of the primary or secondary endpoints as compared to Control treatment.
Safety Analyses	Safety data will be summarized for both treatment groups including frequencies and incidence rates. Safety will be assessed through monitoring of adverse events (AEs), serious adverse events (SAEs), chest CTs or chest X-rays, laboratory tests, oxygenation and ventilatory

parameters, and vital signs.

Table 2: Schedule of Assessments and Procedures

Screening VentaProst - Day 1					VentaProst Days 2-10							End of Study	
Study Procedures	Within 14 Days Prior to Baseline	Baseline 0 Hr	12 hrs	D-2	D-3	D-4	D-5	D-6	D-7	D-8	D-9	D-10/ End Study Treat ment	Day 28 (+/- 2 days)
Written Informed Consent ¹	X												
Demographics	X												
Medical History	X												
Review Inclusion/Exclusion Eligibility Criteria	X	X											
Medication History/ Prior Meds	X												
Physical Examination	X												
Weight/Height ²	X											X	
Randomization		X											
Chest CT Scan or CXR	X						X^3						

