3.3 Study Design

This is a double-blind, placebo controlled study of VentaProst (Active) as compared to placebo (Control). Active is inhaled epoprostenol administered via the VentaProst delivery system in 10 COVID-19 positive patients. Control is inhaled 0.9% sodium chloride solution administered via the VentaProst delivery system in 10 COVID-19 positive patients. Throughout the remainder of the protocol both Active and Control will be referred to as "study drug". This study will evaluate the potential therapeutic benefit of VentaProst in treating patients with COVID-19 who require mechanical ventilation and are at risk for the progression of respiratory and/ or cardiac/circulatory failure. This study will assess the efficacy and safety of VentaProst at an initial dose of 13.6 ng/kg/min (A range from 3.4-30.6 ng/kg/min may be administered as clinically required for a maximum of 10 days at the discretion of the Investigator. Patients will be followed through Day 28 to assess clinical outcomes.

Patients will be consented and randomized to either the Active or Control group within 48 hours of being placed on mechanical ventilation. Informed consent may be obtained after some screening study procedures were collected as part of the patient's standard of care treatment. Patients will be administered study drug using the VentaProst delivery system which allows up and down titration of study drug to achieve hemodynamic and oxygenation stability. The starting dose of study drug will be initiated at 13.6 ng/kg/min. Based on hemodynamic and oxygenation parameters, the dose of study drug can be increased in 3.4 ng/kg/min increments up to a maximum of 30.6 ng/kg/min or down to a minimum of 3.4 ng/kg/min.

All study staff with the exception of the unblinded pharmacist and Sponsor CRA will be blinded to which treatment regimen a patient has been assigned. Titration and weaning will be performed the same for all patients. Study drug will be administered based on the pump rate calculated for active treatment in mL/hr. Titration guidelines are provided in Section 5.3.3 and Table 3.

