4.1 Inclusion Criteria

Patients are eligible for this study if they meet all of the following criteria:

- 1. Women and Men Age ≥18 years old (no upper limit)
- 2. Confirmed COVID-19 positive by a diagnostic test such as molecular or antigen test
- 3. Patients who require invasive mechanical ventilation.
- 4. Enrolled into study within 48 hours of being placed on mechanical ventilation
- 5. Consent or professional consent obtained
- 6. Duration of shortness of breath must be within the previous 14 days.
- 7. Female subjects of childbearing potential must have a negative pre-treatment pregnancy test (serum or urine).
- 8. Received or currently receiving dexamethasone therapy for COVID-19
- 9. Willing and able to comply with treatment schedule and follow-up.

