6.2 Secondary Endpoints

- 1. Improvement in oxygenation defined as any one of the following:
 - Stabilization of PaO2/FIO2 >250
 - Improvement in FIO2 by 50% or improvements ≥15% in S/F, P/F ratio from baseline at 12 hours, Day 5 and Day 10 (or end of treatment)
- 2. Improved clinical outcomes defined as one of more of the following:
 - Time to extubation following the site's extubation protocol

- Free from re-intubation
- Reduction in ICU days
- Reduction in the number of re-admissions to the ICU due to COVID-19 within 28 days
- Reduction in total hospital days
- Mortality [28 days] defined as Cardiopulmonary mortality from all causes

3. Safety and tolerability

 Monitoring of adverse events (AEs), serious adverse events (SAEs), chest CT or Chest X-rays, vital signs, ventilatory/oxygenation parameters, and laboratory tests.

6.3 Exploratory endpoints will include (where available as part of standard of care):

- Change in LDH
- Change in fibrinogen
- Change in WBC count including lymphocytes and neutrophil subsets
- Change in triglycerides
- Change in ferritin
- Change in CRP / ESR
- Change in IL-6
- Change in D-Dimer

Changes in these parameters will be assessed for each patient from baseline to end of study as well as changes between the active and control groups.

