10.3 Analyses Sets

All patients who are enrolled in the study and who receive at least one dose of study drug will be included in the intent-to-treat (ITT) analyses of pharmacodynamic and safety data. All available data will be used and missing data will not be estimated or carried forward in any statistical summary or analyses.

Descriptive summary statistics include the number of patients, mean, median, percent coefficient of variation (% CV) (if required), standard deviation, and minimum and maximum values (quantitative variables) or the number of patients and percentages by category (qualitative variables). Changes will be assessed as the difference between baseline measurements and the appropriate post-dose measurements unless otherwise specified. Mean differences between active and control groups (when available) will be assessed and significance will be determined on the basis of a 95% CI. Individual patient listings of data will also be provided to allow for review of all pharmacodynamic, safety, and tolerability parameters.

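### The ICU re-admission item is a raw count with no at-risk set, so patients who die in the ICU or never leave it get its best score

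*Combined protocol and SAP*

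**What the plan says.** All references are to the current (last) protocol version. Section 4.1 admits only ventilated patients: "Enrolled into study within 48 hours of being placed on mechanical ventilation". Section 5.3.3 starts study drug in the ICU, so every patient begins follow-up there.

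Section 6.2, repeated in 10.6.2 and the synopsis, sets the second secondary endpoint as "Improved clinical outcomes defined as one of more of the following". Six items follow. Three matter here:

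- "Reduction in the number of re-admissions to the ICU due to COVID-19 within 28 days"
- "Reduction in ICU days"
- "Mortality [28 days] defined as Cardiopulmonary mortality from all causes"

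No section limits the re-admission count to patients discharged alive from the ICU, relates it to time spent out of the ICU, or says how death or a continuing stay is scored. The origin of the 28 days is not given. Section 3.3 says only "Patients will be followed through Day 28 to assess clinical outcomes".

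For analysis, the synopsis says "Efficacy will be secondarily determined by summarizing success or failure to meet any of the primary or secondary endpoints as compared to Control treatment", and section 10.3 says "Mean differences between active and control groups (when available) will be assessed and significance will be determined on the basis of a 95% CI". Section 10.1 states that no SAP will be written, so the definition is not completed elsewhere. The Day 28 visit (9.1.3) lists adverse events, mortality and concomitant medications. Neither it nor the schedule of assessments has an entry for ICU admission, discharge or re-admission.

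**The concern.** Re-admission needs a prior live discharge. Read with a window ending at study Day 28, a patient's time at risk is 28 days minus the ICU stay. It is zero for anyone who dies in the ICU or is still there at Day 28. All of these patients contribute zero re-admissions, and fewer counts as better.

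The count therefore mixes two things: how often discharged patients return, and how many patients were discharged and how early. The second part runs against the neighbouring ICU-days and mortality items, because success on those adds patients and days at risk of re-admission.

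Two errors follow. A drug that gets patients out of the ICU can look worse on this item. A drug that prolongs ICU stay or raises ICU mortality can look better on it and, because one item is enough, could literally meet the improved-outcomes definition through it. Mortality is listed separately and is not combined with re-admission, so it does not block that route. The background (2.1) gives mortality of 22% to 62% in the critically ill, so patients who can never be re-admitted may be a large share of the sample.

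**Working it through.** The documents state no re-admission rate, ICU stay or effect size, so there is no plan figure to reproduce. The inputs from the documents are 10 patients per arm, 28 days, and the 22% to 62% mortality range. Everything else below is an assumption.

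**1. Days at risk, simple illustration.** Patient-days at risk = number discharged alive × (28 − mean ICU discharge day).

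- Control, 4 of 10 discharged at mean Day 16: 4 × 12 = 48 of 280 patient-days (17%).
- Active, 6 of 10 discharged at mean Day 14: 6 × 14 = 84 of 280 (30%).
- At the same daily risk the expected counts stand in the ratio 84/48 = 1.75.
- If only the number discharged differs: 60%/40% = 1.5, or 70%/50% = 1.4.

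**2. Absolute size.** At an assumed 0.01 re-admissions per day out of the ICU, 48 × 0.01 = 0.48 against 84 × 0.01 = 0.84 events per arm, a difference of about a third of one event.

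**3. Break-even.** The Active excess disappears if its daily risk is 48/84 = 0.57 of Control's.

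**4. Sensitivity.** A second model takes the share of patients re-admitted as f × mean[1 − exp(−h(28 − t))]. Here f is the share discharged alive, t the ICU discharge day (spread uniformly ±4 days around its mean), and h the daily hazard, equal in both arms. Arms of 10 are compared with exact binomials. At h = 0.01:

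| Scenario (Control vs Active) | Expected per 10 | Ratio | Break-even hazard ratio | Chance Active strictly higher | Tie |
|---|---|---|---|---|---|
| A: 50% at Day 18 vs 60% at Day 15 | 0.47 vs 0.73 | 1.54 | 0.63 | 38% | 41% |
| B: 38% at Day 20 vs 78% at Day 14 | 0.29 vs 1.02 | 3.49 | 0.27 | 55% | 35% |
| C: 60% at Day 18 vs 60% at Day 13 | 0.57 vs 0.83 | 1.47 | 0.67 | 40% | 38% |
| D: 38% vs 78%, both at Day 18 | 0.36 vs 0.74 | 2.05 | 0.47 | 42% | 42% |

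Scenarios B and D take 1 − 0.62 = 0.38 and 1 − 0.22 = 0.78 from the two ends of the background mortality range. They are extremes, not expected arm differences. For h from 0.005 to 0.02 the ratios stay at 1.5 to 1.6 (A), 3.4 to 3.5 (B), 1.4 to 1.5 (C) and 2.05 (D).

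Reading the table with the arms exchanged gives the opposite error: the arm with worse ICU outcomes shows strictly fewer re-admitted patients 38% to 55% of the time.

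**5. Which denominators remove the bias.**

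- Per patient-day out of the ICU, step 2 gives 0.48/48 = 0.84/84 = 0.01, a ratio of 1.00.
- Per patient discharged alive is only a partial repair. It equalises D (0.095 vs 0.095) but not C (0.095 vs 0.139), because earlier discharge still gives longer time at risk.
- Mean days out of the ICU per enrolled patient, before subtracting re-admission days, would be 48/10 = 4.8 against 84/10 = 8.4, which favours the arm with better discharge.

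**The case against.** A reader might infer that an effective drug will show more re-admissions and be judged worse. The documents do not support that, for three reasons.

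- **It is an expectation at equal daily risk, not a certainty.** If the drug also lowers the daily re-admission risk, the direction can reverse. In scenario A a halved hazard gives 0.38 vs 0.47 in favour of Active. With 10 per arm, ties are common and chance often hides the effect.
- **It concerns one item.** The endpoint needs one or more of six, so a drug that shortens ICU stay can still qualify through the ICU-days item or time to extubation. A poor re-admission count cannot cancel that. This answers the penalty on a good drug. It does not answer the opposite error, since the same rule lets a low count stand alone as improvement.
- **The Day 1 origin of the window is an inference.** It is the natural reading: follow-up ends at Day 28, so a 28-day window starting at ICU discharge could not be completed within it. If the window did start at discharge, unequal time at risk would drop out and unequal numbers at risk would remain (1.75 falls to 6/4 = 1.5).

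It is also fair to say that the ratios rest on assumed discharge figures, that restricting the count to re-admissions due to COVID-19 can only lower it, and that the trial is exploratory with about 20 patients. These points limit the severity. They do not supply the missing at-risk set.

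**Conclusion.** The point holds as a bias in one secondary item. Followed as written, the plan gives the best value to patients who die in the ICU or never leave it. At equal daily re-admission risk it is expected to give the higher count to the arm with earlier or more frequent live discharge. The illustrative excess is 1.4 to 1.75 times, or 1.4 to 1.5 if only the number discharged differs; the wider scenarios reach about 3.5 at the extremes of the background mortality range. In absolute terms this is under one event per arm in most scenarios at an assumed 0.01 per day. The bias vanishes or reverses once the drug's daily re-admission hazard falls below roughly 0.27 to 0.67 of Control's, depending on the scenario. Severity is low to moderate. The conclusion rests on equal daily risk, assumed discharge shares and times, and, for the unequal-time part, a window that ends at study Day 28.

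**What to change.** In the synopsis, 6.2 and 10.6.2:

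1. State the origin of the 28-day window; study Day 1 is the natural choice.
2. Compare arms on days alive and out of the ICU from Day 1 to Day 28, with re-admission days subtracted. Death in the ICU or a stay continuing through Day 28 counts as zero days.
3. Report re-admissions descriptively by arm: number of re-admissions, number of patients discharged alive from the ICU, and patient-days out of the ICU.
4. The ICU-days item may stay as a descriptive summary.
5. Add ICU admission, discharge and re-admission dates to the Day 28 data collection (9.1.3 and the schedule of assessments).

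The cost is endpoint wording and a few date fields, which the existing ICU-days and re-admission items need in any case, with no added patient procedure. The downside is that re-admission is no longer a stand-alone comparative endpoint. With so few events expected, little is lost.

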6.4 Appropriateness of Measurements

All clinical assessments are standard measurements commonly used and generally recognized as reliable, accurate, and relevant in studies of cardiac and respiratory function.

7. SAFETY ASSESSMENTS

Safety will be assessed through monitoring of adverse events (AEs) and serious adverse events (SAEs), laboratory tests, chest assessments (Chest CT or Chest X-ray), oxygenation/ventilatory parameters, and vital signs. Safety assessment frequency is shown in the Schedule of Assessments and Procedures.

7.1 General Safety Procedures

7.1.1 Vital Signs and Weight Measurements

Vital sign measurements, including systolic blood pressure (SBP), diastolic blood pressure (DBP), heart rate (HR) [beats per minute], respiratory rate (breaths per minute), and body temperature (in Celsius) will be obtained twice daily Days 1-10 or as clinically indicated. Weight (kg) will be obtained at the time of Screening and at Day 10 or end of VP treatment. Height will be obtained at the time of Screening. If unable to obtain height, the study staff will use the best reported historical height from patient or LAR.

7.1.2 Physical Examination

A physical examination will be conducted at the screening visit and may include assessments of general appearance; skin and lymphatics; eyes, ears, nose, throat; cardiovascular system; respiratory system; abdomen/gastrointestinal system; urological system; musculoskeletal and neurological systems. Other body systems may be examined as clinically indicated.

7.1.3 Laboratory Measurements

Clinical laboratory measurements to b	e performed are listed below. The Schedule of Assessments			
and Procedures shows the time points a	t which blood will be collected for clinical laboratory tests and			
pregnancy testing. The Baseline for laboratory tests is the Screening assessment.				
Category	Parameters			
	H 11: 1 / PDC WDC '4 1'CC / 1			

Category	Parameters	
Hematology-CBC with diff	Hemoglobin, hematocrit, RBC, WBC with differential (neutrophils, lymphocytes, monocytes, eosinophils, basophils), platelets	
Full Chemistry Panel		
Electrolytes	Sodium, potassium, chloride, bicarbonate, calcium	
Liver function tests	AST, ALT, AP, total bilirubin	
Renal function parameters	BUN, creatinine	
Coagulation Studies	PT/PTT	
Other	Serum or urine pregnancy test, COVID-19 diagnostic test, Troponin, and BNP (fibrinogen, ferritin, LDH, Triglycerides, D-Dimer, IL-6, ESR,CRP may be obtained if the patient's standard of care warrants the tests)	

7.1.4 Chest Assessments

A Chest CT or Chest X-ray will be obtained at Screening and between days 3 to 8 as clinically indicated.

7.1.5 Time Prone Protocol

The time prone protocol is a standard of care in OSU's ICU. This will be in place for all days that patients are within the ICU.

7.2 Adverse Events

7.2.1 Definitions

Adverse events are any untoward medical occurrence in a patient administered a pharmaceutical product and which does not necessarily have to have a causal relationship

with this treatment. For the purposes of this study, this will include unanticipated medical events in the judgment of the investigator. *A pre-existing condition* or symptom is one that is present at the start of the study and is reported as part of the patient's medical history. A pre-existing condition or symptom should be reported as an AE only if its frequency, intensity or character worsens during study treatment.

All AEs that occur from the time of the first dose of study medication through the End of Study (Day 28) will be recorded and reported as Treatment-Emergent Adverse Events (TEAE). All AEs must be appropriately documented in the patient's medical chart/source documentation and on the DCFs. When known, investigators should report syndromes rather than list symptoms associated with the syndrome.

All AEs that are ongoing at the conclusion of the study should be followed until: a) resolution/stable sequelae; b) the Investigator determines that it is no longer clinically significant; or, c) the study patient is lost to follow-up. If no follow-up is provided, the Investigator must provide a written justification.

7.2.2 Adverse Events of Special Interest (AESI)

Pulmonary edema and pulmonary hemorrhage are AEs of special interest due to the mode of action of epoprostenol. If an AE of special interest occurs, the Sponsor will be notified of this occurrence within 24 hours.

7.2.3 Grading of Adverse Events

The severity of each AE will be categorized using the following criteria:

- Grade 1 (Mild): usually transient; requires no special treatment and does not interfere with the patient's daily activities.
- Grade 2 (Moderate): produces a low level of inconvenience to the patient and may interfere with daily activities. These AEs are usually ameliorated by simple therapeutic measures.
- Grade 3 (Severe): interrupts daily activity and requires systemic drug therapy or other medical treatment.

7.2.4 Relationship to Study Medication/Study Device/Procedure

The Investigator must assess the relationship of each reported AE. The Investigator must make an assessment of the relationship of the AE to the study drug/study device/procedure using the following scale:

- Unrelated: The AE is definitely not or unlikely to be associated with study medication/study device/procedure and is judged due to causes other than the study medication/study device/procedure.
- Related: The AE is possibly or probably related with study medication/study device/procedure.

7.2.5 **AE Outcomes**

The following terms and definitions are used in assessing the final outcome of an AE:

- Recovered/Resolved The patient has fully recovered, or by medical or surgical treatment, the condition has returned to the level observed at the first trial-related activity.
- Recovering/Resolving The condition is improving and the patient is expected to recover from the event.
- Recovered/Resolved with sequelae The patient has recovered from the condition, but with lasting effect due to a disease, injury, treatment or procedure. If a sequela meets an SAE criterion, the AE must be reported as an SAE.
- Not recovered/Not resolved The condition of the patient has not improved and the symptoms are unchanged, or the outcome is not known at the time of reporting.
- Fatal This term is only applicable if the patient died from a condition related to the reported AE. Outcomes of other reported AEs in a patient before he/she died should be assessed as "recovered", "recovering", "recovered with sequelae" or "not recovered". An AE with fatal outcome must be reported as an SAE.

7.2.6 Laboratory Test and other Test Abnormalities as Adverse Events

A laboratory or other test (chest assessments, vital signs) abnormality should be reported as an AE if the Investigator considers the abnormality an AE or if the abnormality is associated with accompanying symptoms, requires medical/surgical intervention, leads to a change in study treatment, or results in discontinuation from the trial. When possible, syndromes not laboratory values, should be reported as AEs. For example, elevated hepatic transaminases associated with hepatitis should be reported as "hepatitis" and decreased hemoglobin and hematocrit requiring iron supplementation should be recorded as "anemia." Prior to reporting as an AE, abnormal tests should be repeated to verify the accuracy of the original result.

